2.2 BACKGROUND

HBV infection is a major cause of both acute hepatitis and chronic liver diseases, including cirrhosis and hepatocellular carcinoma. Approximately 257 million people worldwide are living with chronic HBV infection (defined as hepatitis B surface antigen [HBsAg] positive). In 2015, HBV resulted in an estimated 887,000 deaths, mostly from complications including cirrhosis and hepatocellular carcinoma (WHO 2020; EASL 2017).

Currently, there are two classes of drugs available for the treatment of chronic HBV: subcutaneously administered interferon preparations and orally administered nucleos(t)ide analogues (NUCs). Although both types of treatment can induce the loss of

hepatitis B e antigen (HBeAg) with the development of anti-HBeAg antibody (serological response), the suppression of HBV deoxyribonucleic acid (DNA) to an undetectable level by sensitive polymerase chain reaction (PCR) methods (virological response), and are able to normalize liver transaminases levels (biochemical response), neither treatment achieves a high rate of functional cure. HBsAg loss only occurs in approximately 3% of patients after one year of treatment and in <15% after 1 to 5 years follow-up ([EASL 2017](#)). In addition, interferon-based therapies are associated with many side effects, while NUCs frequently require prolonged or possibly life-long therapy, and some are associated with a high risk of viral resistance. Thus, there is an unmet medical need for a therapy that can achieve a higher rate of functional cure, has a finite treatment duration, and is well tolerated.

RO7049389 is an inhibitor of HBV capsid assembly and belongs to the well-studied class of heteroaryldihydropyrimidine compounds. This class of compounds induces formation of abnormal HBV core protein aggregates, which are subsequently recognized and depleted. Depleting functional core protein results in interruption of viral assembly and inhibition of HBV replication.

Three Phase I clinical studies of RO7049389 have been completed: YP39364 (Parts 1 and 2), YP39406, and YP40218.

In Study YP39364, Parts 1 and 2 were randomized, Sponsor open, Investigator blinded, and participant-blinded. Part 1 was a single-ascending dose (SAD) and multiple-ascending doses (MAD) investigation of the safety, tolerability, and PK of RO7049389 following oral administration in HVs, including the effect of food on the PK of single-dose RO7049389 and the effect of multiple-dose RO7049389 on the PK of midazolam. Part 2 evaluated the safety, tolerability, PK, and pharmacodynamics (PD) of orally administered RO7049389 in patients chronically infected with HBV.

Study YP39406 was a single center, randomized, Sponsor-open, Investigator-blinded, participant-blinded, placebo-controlled, SAD, and MAD study to investigate single and multiple doses of RO7049389 in HVs of Chinese descent for comparison with HVs in Part 1 of Study YP39364.

Study YP40218 was a DDI study to assess the effects of RO7049389 as an OATP inhibitor on the PK of OATP substrate (pitavastatin as a probe drug).

A detailed description of the chemistry, pharmacology, efficacy, and safety of RO7049389 is provided in the [RO7049389 Investigator's Brochure \(IB\)](#).

2.3 BENEFIT/RISK ASSESSMENT

This study has the principal aim of characterizing the MB, metabolite identification, metabolism routes, rates of elimination, and absolute oral BA of RO7049389, in a population of HVs. There will be no therapeutic benefit for the HVs participating in the study. However, assessment of the MB and absolute BA of RO7049389 brings valuable information for the development of RO7049389.

The total burden of radioactivity associated with the dose planned in this MB cohort (not more than 59.3 μ Ci; 2.2 MBq) is 0.57 mSv which is well below the maximum effective dose of 1 mSv to fall into, International Commission on Radiological Protection ([ICRP](#)) Category IIa.

Furthermore, an assessment was conducted to determine whether there is any impact of the COVID-19 pandemic on the benefit/risk assessment of this study protocol, including but not limited to the participants in this study and the study treatment evaluated. Based on that assessment, no impact is anticipated and the existing safety monitoring and management guidelines, and risk mitigation measures provided in the study protocol are considered adequate.

More detailed information about the known and expected benefits in the context of potential risks and reasonably expected AEs of RO7049389 is provided in the [RO7049389 IB](#).

2.3.1 COVID-19 Related Risks and Risk Mitigation Measures

The following risks and risk mitigating measures apply to parts of the study, which will be conducted during the coronavirus disease 2019 (COVID-19) pandemic.

2.3.1.1 IMP-related Risk

Against the background of the COVID-19 pandemic, the potential risk of a participant developing COVID-19 has been considered in terms of the risk-benefit evaluation. The mode of action of the investigational medicinal product (IMP)—as an inhibitor of HBV capsid assembly – has been considered alongside available pre-clinical and clinical data (including class effects) and it is considered that a participant would not be at increased risk of either becoming infected with severe acute respiratory syndrome coronavirus 2 (SARS-CoV-2; the virus that causes COVID-19) or experiencing a more severe illness. That is, the IMP has no known immunomodulatory effect that would confer an increased risk to HVs enrolled in the study.

2.3.1.2 General COVID-19 Related Risk Mitigation Measures

General risk mitigation against COVID-19 will be implemented in accordance with Quotient Sciences clinical unit's monitoring and prevention-control measures.

COVID-19 testing may be performed on the basis of current infection rates and availability of tests. If required, testing will comprise an antibody blood test performed at screening, and an antigen PCR test performed at screening, the day before admission to each treatment period, and discharge or the day before discharge from each treatment period. Testing time points may be changed and additional time points may be added throughout the study as required. The decision on COVID-19 testing and the definition of the testing time points will be agreed by the study team and documented in the Investigator site file (ISF) via the Clinical Kick-Off Meeting minutes.

The risk mitigation measures, where applicable, will be amended on the basis of emerging government guidance.

2.3.1.3 Assessment Regarding COVID-19 Vaccination

Against the background of the COVID-19 pandemic, the risk assessment of the effect of the IMP RO7049389 and concomitant administration of a COVID-19 vaccination has been evaluated for this study. The mode of action of the IMP – as an inhibitor of HBV capsid assembly – has been considered alongside available pre-clinical and clinical data (including class effects) and it is considered that COVID-19 vaccinations are simple concomitant medicines with no interaction with the IMP. However, all concomitant medications are prohibited within 14 days prior to the first dosing or within 5 half-lives

of the medication prior to the first dosing until after collection of the final sample (Section 6.5.2). This is due to the nature and short duration of the study, but not for safety reason. As a mass balance and absolute bioavailability study conducting in healthy volunteers, prohibition of all concomitant medications is required to ensure the integrity of the study by minimizing any potential physiological changes.

3. OBJECTIVES AND ENDPOINTS

	Objectives	Endpoints
Primary	
 To characterize the mass balance (MB), routes, and rates of elimination of [¹⁴C] RO7049389. To determine the absolute oral bioavailability (BA) of RO7049389. 	
 Percentage of dose excreted in urine. Percentage of dose excreted in feces. Absolute oral BA for RO7049389.
Secondary		
 •
	
 To determine the plasma concentration of RO7049389, its identified three metabolites (RO7121986, RO7255420, and RO7255422), total drug-related radioactivity and related pharmacokinetic (PK) parameters. 	
 C_{max}, AUC_{last}, AUC_{0-inf}, t_{max}, CL/F, CL, CL_r, Ae, V/F, and $t_{1/2}$ of RO7049389 and its identified three metabolites, and total drug-related radioactivity, if appropriate.
	
 To identify and quantify circulating and excreted metabolites of RO7049389 in plasma, urine, and fecal samples based on radioactive metabolic profiling. 	
 A metabolic profile for RO7049389 and metabolites, and their structural elucidation, if appropriate. C_{max}, AUC_{last}, AUC_{0-inf}, t_{max}, CL/F, CL_r, Ae, V/F and $t_{1/2}$ of other major metabolites related radioactivity, if appropriate.
	
 To evaluate the safety and tolerability of one or two single-doses of RO7049389 in healthy participants. 	
 Adverse events (AEs), clinical laboratory values, vital signs, electrocardiogram (ECG), and physical examination.

OBJECTIVES AND ENDPOINT (CONT.)

Exploratory		
	
• To determine whether genes relating to drug-metabolizing enzymes and/or drug transporters affect the PK and/or the safety profile of RO7049389.	
• The pharmacogenetics of metabolizing enzymes (CYP3A4, UGT1A3) and transporters (OATP1B) possibly involved in the absorption, distribution, metabolism, and excretion of RO7049389 and its major metabolites.
	
• To determine the relative BA of RO7121986.	
• C_{max}, AUC_{last}, $AUC_{0-\infty}$ of RO7121986 after oral and intravenous (IV) administration of RO7049389.

4. STUDY DESIGN

4.1 OVERALL DESIGN

This is an open-label, two-cohort (i.e., a MB cohort and an absolute BA cohort), single-dose study designed to evaluate the MB and absolute BA of RO7049389 in HVs.

An overview of the study design is provided in Section 1.2. The investigational medicinal products (IMPs) required for completion of this study will be [¹²C] RO7049389 tablet, 200 mg, [¹⁴C] RO7049389 oral suspension, 600 mg (NMT 2.2 MBq), and [¹³C] RO7049389 solution for infusion, 20 μ g/mL.

Male participants in the MB cohort will receive a 600 mg dose of [¹⁴C] RO7049389 as an oral suspension under fasted conditions. Participants will then receive 100- μ g dose of [¹³C] RO7049389 administered as a 10-minute intravenous (IV) infusion, 2 hours after the oral dose of [¹⁴C] RO7049389.

In the absolute BA cohort, each participant will take part in both Period 1 and Period 2. Male or female participants in Period 1 of the absolute BA cohort will receive a 600 mg dose of [¹²C] RO7049389 administered orally as a clinical formulation under fasted conditions. Participants will then receive a 100- μ g dose of [¹³C] RO7049389 administered as a 10-minute IV infusion, 2 hours after the oral dose of RO7049389.

After a washout period of at least 7 days, in Period 2, male or female participants will receive a 1000 mg dose of [¹²C] RO7049389 administered orally as a clinical formulation under fasted conditions. Participants will then receive 100 μ g of [¹³C]

RO7049389 administered as a 10-minute IV infusion, 2 hours after the oral dose of RO7049389.

4.1.1 Discharge Criteria for Mass Balance Cohort

In the MB cohort, total urine and feces will be collected at appropriate time intervals in the unit until the following discharge criteria are met:

At least 90% of the total radioactivity has been recovered in urine and feces, or < 1% of the administered dose excreted in two consecutive 24-hour urine and fecal samples, whichever is shorter.

All participants are required to stay in the unit at least until the morning of Day 8. If the results from the samples collected for up to 144 hours show that all participants meet the discharge criteria, then all participants are discharged from the unit on Day 8.

If the samples collected up to 144 hours show that not all participants meet the discharge criteria, then all participants will be kept in the unit to collect additional samples until the results from the samples collected for up to 192 hours show that all participants meet the discharge criteria. All participants are therefore discharged either on Day 9 or on Day 10, depending on when the discharge criteria are met by all participants.

If the samples collected up to 192 hours show that not all participants meet the discharge criteria, then all participants will be kept in the unit for a maximum of 2 additional days (until the morning of Day 12) to collect additional samples. Based on the results from the samples collected up to 240 hours, participants are allowed to be discharged on an individual basis if the discharge criteria are met.

The remaining participants who do not meet the discharge criteria by the morning of Day 12 will be discharged from the unit and will be required to collect further samples (urine/feces) at home for up to a maximum of five additional days, until the discharge criteria are met.

4.1.2 Length of the Study

The identity of the participants will be confirmed at admission and pre-dose. In addition, the ongoing eligibility of participants will be re-assessed at admission/pre dose, as described in Section 5.1 and Section 5.2. Admission/pre-dose safety procedures such as safety bloods tests, ECGs, vital signs, urinalysis, and drugs of abuse tests can be repeated as clinically indicated under the discretion of Investigator or sub-investigator if there is a concern regarding a participant's safety or eligibility to participate in the clinical trial. Reserve participants for the first dose occasion, in any group, will not require admission procedures to be repeated if dosing is within 2 days.

The participants will be admitted to the clinical unit on the morning before dosing (Day -1).

In addition, participants may be required to visit the clinical unit on the day before admission for each treatment period for SARS-CoV-2 antigen tests (if required).

In the MB cohort, the total duration of the study for each participant will be about 8 weeks, divided as follows:

- Screening: Up to 28 days.
- In-clinic period: Day -1 to the day when the discharge criteria (See Section 4.1.1) are met. This is up to a maximum of 12 days.
- Safety follow-up: One call on Day 29 ± 3.

In the absolute BA cohort, the total duration of the study for each participant will be *at least 9 weeks*, depending on the duration of the washout period, divided as follows:

- Screening: Up to 28 days.
- In-clinic period: Days -1 to 4 for both Periods 1 and 2.
- Washout period: Defined as from Period 1 Day 1 to Period 2 Day 1 and lasts at least 7 days.
- Safety follow-up: One call on Period 2 Day 29 ± 3.

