8.3 ADVERSE EVENTS AND SERIOUS ADVERSE EVENTS

The definitions of an AE or SAE can be found in [Appendix 2](#). The NSAESI are discussed in Sections [8.3.6](#).

The Investigator and any qualified designees are responsible for ensuring that all AEs (including assessment of seriousness, severity, and causality; see [Appendix 2](#)) are recorded on the AE eCRF and reported to the Sponsor in accordance with instructions provided in this section and in [Appendix 2](#).

Procedures used for recording AEs are provided in [Appendix 3](#):

- Diagnosis versus signs and symptoms:
 - Infusion reactions
 - Other AEs
- AEs occurring secondary to other events
- Persistent or recurrent AEs
- Abnormal laboratory values

- Abnormal vital sign values
- Abnormal liver function tests
- Deaths
- Preexisting medical conditions
- Hospitalization or prolonged hospitalization

8.3.1 Time Period and Frequency for Collecting Adverse Event and Serious Adverse Event Information

The method of recording, evaluating, and assessing causality of AEs and SAEs and the procedures for completing and transmitting SAE reports are provided in [Appendix 2](#).

Investigators will seek information on AEs at each participant's contact. All AEs, whether reported by the participant or noted by study personnel, will be recorded in the participant's medical record and on the AE eCRF as follows:

After informed consent has been obtained **but prior to initiation of study treatment**, only SAEs caused by a protocol-mandated intervention should be reported (e.g., SAEs related to invasive procedures such as biopsies). Any other AE should not be reported.

After initiation of study treatment, all AEs, regardless of relationship to study treatment, will be reported until 28 days after the last dose of study treatment.

Post-study AEs and SAEs: The Investigator is not required to actively monitor participants for AEs after the end of the AE reporting period (28 days after the last dose of study treatment).

However, if the Investigator learns of any SAE (including a death) or other AEs of concern that are believed to be related to prior treatment with study treatment, at any time after a participant has been discharged from the study, and the Investigator considers the event to be reasonably related to the study treatment or study participation, the Investigator must promptly notify the Sponsor. For the procedure of reporting, see [Appendix 2](#).

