8.9.2 Assessments during Treatment

Under no circumstances, will participants who enroll in this study and have completed treatment as specified, be permitted to re-enroll in the study.

All assessments must be performed as per the SoAs (Section 1.3). Assessments scheduled on the day of study treatment administration should be performed prior to administration of study treatment, unless otherwise noted in the SoAs.

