8.9.3 Assessments at Study Completion/Early Termination Visit

Participants who complete the last dose administration or discontinue from the study early will receive a follow-up call 29 ± 3 days after the last dose of study treatment. The follow-up call will be reported as the study completion visit in eCRF.

In case of early termination of a participant, a blood sample for PK assessment of RO7049389 should be collected at the time of discontinuation. Please also see the SoAs tables (Section 1.3) for activities that are required to be performed in case of an early termination.

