8.9.4 Follow-Up Assessments

After the study completion/early termination visit, AEs should be followed as outlined in Sections 8.3.1 and 8.3.3.

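### The single scheduled safety call (Day 29±3) may be made up to 3 days before the 28-day adverse event reporting period ends, with no later scheduled contact at which AEs are sought

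*Combined protocol and SAP*

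**What the plan says.** **AE period.** Section 8.3.1 states that, once treatment has started, all AEs "will be reported until 28 days after the last dose of study treatment". It adds: "The Investigator is not required to actively monitor participants for AEs after the end of the AE reporting period". On how AEs are found, it says "Investigators will seek information on AEs at each participant", that is, whenever the site is in contact with the participant.

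**Scheduled call.** For the MB cohort, Section 4.1.2 has "Safety follow-up: One call on Day 29" with a tolerance of 3 days either way. For the absolute BA cohort it is Period 2 Day 29±3. The synopsis (Section 1.1) and Tables 1 and 3 agree. The end-of-study text in Sections 1.1 and 4.4 expects the last observation 28±3 days after the last dose.

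**Section 8.9.3.** Participants who complete the last dose or "discontinue from the study early will receive a follow-up call 29"±3 days after it. The same section says: "The follow-up call will be reported as the study completion visit in eCRF".

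**After the call.** Section 8.9.4 says "AEs should be followed as outlined in Sections 8.3.1 and 8.3.3". It schedules no further contact.

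**Which text governs.** Section 8.9.2, on assessments during treatment, says "All assessments must be performed as per the SoAs".

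**The concern.** The sponsor chose a 28-day AE period and an ascertainment method that relies on asking at each contact. The last planned occasion to ask may fall inside that period instead of at or after its end. After an early call, an AE that starts in the remaining 1 to 3 days must still be reported, but the site hears of it only if the participant comes forward or an unscheduled contact happens. At stake is complete AE capture at the end of the window. Safety and tolerability is a secondary objective, and Section 9.3.2 summarises it descriptively. The mass balance and bioavailability endpoints do not depend on the date of this call.

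**Working it through.** **Inputs**
- Day convention: Table 1, footnote i, equates 264 hours post-dose with Day 12.
- Last dose: the IV infusion, 2 hours after the oral dose, on Day 1 (MB) or Period 2 Day 1 (absolute BA); Section 6.1.2.
- End of AE period: 28 days after the last dose; Section 8.3.1.
- Call: Day 29±3 (Sections 1.1 and 4.1.2, Tables 1 and 3); 29±3 days after the last dose (Section 8.9.3).

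**Step 1: day convention.** 264 / 24 = 11 days after dosing = Day 12. So days after dosing = study day − 1.

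**Step 2: reproduce the plan's own figure.** Day 29±3 runs from Day 26 to Day 32. Subtracting 1 gives 25 to 31 days after the last dose, which is 28±3. This matches Sections 1.1 and 4.4 exactly.

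**Step 3: compare each window with day 28.** Largest gap = 28 − earliest permitted day.

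| Source | Days after last dose | Permitted days before day 28 | Largest gap |
|---|---|---|---|
| Schedule, Day 29±3 | 25 to 31 | 25, 26, 27 (3 of 7) | 28 − 25 = 3 days |
| Section 8.9.3, 29±3 days | 26 to 32 | 26, 27 (2 of 7) | 28 − 26 = 2 days |
| Proposed, Day 29 (+3) | 28 to 31 | none (0 of 4) | 28 − 28 = 0 days |

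The fractions count permitted calendar days. They are not probabilities that a call is made early.

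**Step 4: the two existing windows.** They share days 26 to 31, which is 6 of 7 days. Section 8.9.3 is centred one day later than the schedule.

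**Step 5: look for any other contact that covers the gap.** MB participants who do not meet the discharge criteria may collect samples at home for up to 5 days after Day 12 (12 + 5 = Day 17). This is not a safety contact and ends well before Day 26. Unscheduled visits are not routine. Section 7.1 asks participants who stop treatment early to return for an early termination visit, but does not date it relative to day 28.

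**The case against.** The strongest case on the other side is that this is an ordinary visit tolerance. The nominal call falls exactly at the end of the AE period, and Sections 1.1 and 4.4 state the 28±3 openly, so the tolerance looks deliberate. Section 8.3.1 says when active monitoring may stop; it does not demand a scheduled contact on or after day 28. Late events are also not especially expected: doses are single, participants are healthy, the minimum washout is 7 days, and plasma sampling for parent drug and metabolites ends at 72 hours. All of this stands, and it keeps the point small. It does not identify any contact that covers the days after an early call.

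Three stronger readings are tempting, and the documents do not support them:

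- **A reader might infer that AE collection stops at the call.** It does not. Sections 8.3.1 and 8.9.4 keep the reporting duty running, and Section 8.3.1 also requires notification of related SAEs or AEs of concern learned of later. What lapses is scheduled prompting.
- **A reader might infer that Section 8.9.3 leaves the site with an unresolved conflict.** It is a one-day wording slip. The windows share 6 of 7 days, and Sections 8 and 8.9.2 point to the schedule for timing.
- **A reader might infer that absolute BA participants who stop after Period 1 have no follow-up rule,** because Table 3 dates the call only by Period 2. Section 8.9.3 covers early discontinuation and ties the call to the last dose, and Section 7.1 adds the early termination visit.

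The objection that a narrower window leaves less room to reach people is also fair. It is the real price of the change.

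**Conclusion.** The point holds as a minor, inexpensive improvement. A compliant call can precede the end of the 28-day AE period by 1 to 3 days, with no later scheduled contact at which AEs are sought. The maximum is 3 days per participant on the schedule's count, and a call on Day 29 leaves no gap. The effect is confined to AE ascertainment.

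This rests on counting in whole days with dosing on Day 1, and on the call being the last routine contact, as its status as the completion visit implies. The documents do not say how often calls are made early or how often AEs start this late, so the number of missed AEs cannot be estimated, and nothing suggests it would be large.

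**What to change.** - Set the call to Day 29 (+3) in Sections 1.1 and 4.1.2 and in Tables 1 and 3 (Period 2 Day 29 (+3) for the absolute BA cohort).
- Change Section 8.9.3 and the end-of-study text in Sections 1.1 and 4.4 to 28 (+3) days after the last dose. This also removes the one-day slip.
- For absolute BA participants who discontinue after Period 1, make the call 28 (+3) days after the Period 1 dose. The washout has a 7-day minimum and no maximum, so someone may leave later than that; in that case make the call at the time of discontinuation. Keep the Section 7.2 rule that there is no follow-up once consent is withdrawn.

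The call then falls 28 to 31 days after the last dose for everyone who completes dosing, and the latest scheduled day is unchanged.

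**Cost.** The permitted window shrinks from 7 days to 4, so there is less room to reach people, and some of the 22 planned participants (6 + 16, plus any absolute BA replacements) are called up to 3 days later. The wording edits need an amendment and could go in with the next one. No visit, sample or procedure is added.
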